**A Feasibility Study: Understanding and Altering Pain Expectations in Subjects with
Osteoarthritis of the Knee or Hip**

11/6/2014

NCT02155257

Why a feasibility study

In May we submitted a Program Project Grant (P01) application to the NIH. This \$10 million effort would fund a group of laboratory and clinical investigations to better understand and prevent the problem of chronic pain and disability after major surgery. Although we provided some preliminary data with that application, we expect that additional feasibility data will be required for the application to reach a level of priority high enough for funding. The current IRB application is to collect those feasibility data in time for a November, 2014 revision.

Both chronic pain and disability after total knee replacement surgery are predicted by negative cognitive-affective state, characterized by depression, anxiety, and a cognitive style dominated by catastrophizing. How this negative state results in chronic pain and disability is not known, but we hypothesize that it causes dysfunction of the release of the neurotransmitter, norepinephrine in several regions of the brain, mid-brain, and spinal cord that are important to many processes involved in recovery from surgery. In the P01 grant application we propose to test these circuits in animals and to study patients after total knee replacement as well as those with moderate daily pain and osteoarthritis who are not undergoing surgery. This protocol is to generate feasibility data for the osteoarthritis study in time for the Nov, 2014 revision, if it is needed.

Background

The locus coeruleus (LC) as a regulator of gain. The LC is a small collection of neurons in the pons which provides the exclusive or near-exclusive noradrenergic innervation to the cortex, spinal cord, and mid-brain. Although involved in many processes, the diffuse cortical projections from the LC are key regulators of gain of overall brain network function and response (Eldar, 2013). As opposed to amplification, which results in increased signals from all components of a complex circuit, increasing gain results in increased dominance of strong signals at the expense of weak signals (Figure 1). In humans, increased LC activity and inferred gain sharpens connectivity as determined by fMRI such that weak connections become weaker and strong connections become stronger (Eldar, 2013). That study compared learning with abstract versus visual tests, and showed that increased gain resulted in stronger reliance on the individual's preferred learning style. In other words, when gain was low, individuals learned by either style, visual or abstract, but when gain was high, they relied much more heavily on their preferred style. Those who rated themselves better as visual learners became even better at the visual learning tasks and worse at the abstract learning tasks under high gain conditions, whereas the abstract learners did the opposite. Thus, gain determines how much one applies their preferred mode of response to a stimulus, situation, or task.

[figure not shown]

Figure 1: Gain sharpens output by altering input strength (Eldar, 2013)

Pain is a recurrent, powerful stimulus after surgery or in those with advanced arthritis, and the gain concept suggests that experience of intermittent pain reflects not just how the underlying personality factor interacts with the stimulus itself, but also how high the gain is. Data from an ongoing preliminary study in the CRU at Wake Forest in healthy volunteers receiving experimental pain stimuli support this idea.

The pupil reports LC activity and gain. Studies in animals with electrodes implanted in the LC and in humans with fMRI imaging of the LC suggest that changes in pupil diameter faithfully report LC activity (Gilzenrat, 2010; Payzan-Lenestour, 2013; Eldar, 2013). Our ongoing study in healthy volunteers asked how pupil responses could predict experience of pain from experimental stimuli.

In this ongoing study we have examined pupil responses to phasic noxious heat stimuli to date in 19 normal volunteers and 4 subjects with migraine (but not in the presence of a headache). Studies were performed in a room with constant, low ambient light so that both constriction and dilation of the pupil could be observed. Pupil diameter was continuously monitored by an infrared camera (Eye-Trac™ system; Applied Science Laboratories) with the subject's chin resting on a chin rest and gaze on a fixed object presented on a monitor. A 4 cm² Peltier-controlled thermode was placed on the calf, with temperature maintained at 35°C and 5 sec stimuli at various temperatures applied every 30 sec. Subjects reported pain intensity with a visual analog scale (VAS) from 0 (no pain) to 100 (worst pain imaginable). Increasing probe temperature to 50°C resulted in pain report and pupil dilation, the former with a longer lag (Figure 2, typical response). As previously described with other stimuli (Chapman, 1999; Oka, 2007), there was a direct relationship between pupil dilation and noxious heat temperature as well as VAS pain intensity and unpleasantness.

We next examined the relationship between pupil response and pain report as a function of affective distress. We estimated affective distress as the sum of scores to the pain catastrophizing scale, the CSED depression scale, the state trait anxiety inventory, and the pain anxiety symptom scale and linearly regressed this on pain report. The residual from the regression line for each individual was related to baseline pupil diameter as a measure of tonic LC activity. Despite there being a very small range of affective distress in this largely normal population, the residual (tendency to adhere to cognitive-affective state in pain reporting) was significantly related to baseline pupil diameter (Figure 3).

Expectations alter pain experience. We are also manipulating expectations in this study of healthy volunteers. Pain stimuli are first presented as a random series without cues, then as a series preceded by 6 sec with an auditory cue to indicate whether the stimulus would be mildly (47°C) or moderately (50°C) painful, then as a series with 20% of the cues incorrect. So far we have observed a mild, but highly significant reduction in pain from random to cued condition, consistent with a recent report on the role of uncertainty in pain reporting (Yoshida, 2013). During miscuing, there was a greater effect of negative expectations (expect less pain) than positive ones (expect more pain), as previously reported (Koyama, 2005). In the proposed

[figure not shown]

Figure 2: Time course of heat stimulus and of VAS and pupil responses

[figure not shown]

Figure 3: Relationship between resting pupil diameter and pain reporting by affective distress

study we gather feasibility data in a clinical population (patients with moderate osteoarthritis of the hip or knee) to test whether we can manipulate expectations on pain in this population.

Gabapentin and modafinil to increase LC activity and gain. In animals and humans, the alertness enhancing drug, modafinil (Provigil™) increases tonic LC activity and increases pupil diameter. Although large doses of this drug (800 mg) can increase blood pressure and heart rate, this has not been observed in these studies of over 100 people who received 200 mg (Hou, 2005; Nikolaou, 2008; Minzenberg, 2008; Schmaal, 2013; Geng, 2013). For this reason, we will examine the effects of modafinil, 200 mg, on pupil diameter and its effect to alter pain reporting as a function of baseline state by increasing gain.

A more relevant drug to the question of chronic pain after surgery is gabapentin, and some clinical trials have suggested that perioperative treatment of this drug can reduce the incidence of this problem (Schmidt, 2013). In the NIH application we propose to test gabapentin rather than modafinil because our previous work with direct measures in rats and cerebrospinal fluid norepinephrine sampling in humans is consistent with gabapentin activating LC in both species (Hayashida, 2007). The pupil measurements in this feasibility study will more directly assess whether gabapentin does indeed increase LC activity in humans. Should it fail to demonstrate a reasonable effect size to dilate the pupil, we will revise the NIH application to study modafinil rather than gabapentin. As such, these preliminary data are very important to the design of the final study.

Study Design.

Hypotheses: (1) Gabapentin and modafinil will increase resting pupil diameter with a moderate effect size in patients with osteoarthritis; (2) Expectations will modify pain experience with a moderate effect size in these patients

Study design: Single-center, randomized, controlled study of gabapentin, modafinil, and placebo in 30 subjects (10 per group) with moderate osteoarthritis pain of the hip or knee or healthy individuals without pain

Primary outcome measures: (1) Resting pupil diameter and response to noxious stimuli after study drug; (2) Interaction between resting pupil diameter and correlation of cognitive-affective state to pain reporting.

Inclusion criteria: Adult, nonpregnant adults scheduled with moderate pain (verbal score of $\geq 4 \leq 7$ on 0-10 scale for average pain intensity with normal activity) from osteoarthritis of the knee or hip, or healthy individuals without pain, American Society of Anesthesiologists physical status 1-3, able and willing to perform the study procedures, including sitting in a chair for 45 min. Individuals must be able to read.

Exclusion criteria. (1) Inability to complete questionnaires; (2) Pregnancy; (3) Currently taking gabapentin or > 50 mg morphine equivalents/day; (4) advanced or unstable cardiac, pulmonary, renal or hepatic dysfunction; (5) history of previous eye surgery; (6) psychotic disorder or a recent psychiatric hospitalization.

Catastrophizing-Optimism continuum assessment. Prior to the initiation of experimental procedures, each participant will be administered the battery of questionnaires Table 1. From these questionnaires, we will place each participant on a dimensional continuum that describes their general cognitive style. We will use multidimensional scaling (MDS) to force catastrophizing and optimism as 2 ends of this continuum (Figure 4). These two constructs

describe cognitive styles that are strongly inversely associated with each other; MDS will provide the optimal weights to best order individuals on this latent scale. Studies have examined the interplay of these constructs with other psychological concepts such as acceptance, pain-related disability and psychosocial adjustment and have found that both are reliably associated with the positive and negative aspects of the adjustment to pain.

Study procedures: A total of 30 subjects with moderate average daily pain from osteoarthritis of the knee or hip or subjects with no pain will be recruited and will come to the clinical research unit at Wake Forest. Informed consent will be confirmed and they will complete the questionnaires. We will take a verbal medical and medication history and obtain blood pressure and heart rate measurements. Verbal pain intensity report (0-10 from no pain to worst pain imaginable) will be obtained from 5 sec heat stimuli, separated by 30 sec, delivered to a nonpainful area of skin on the arm as described in preliminary data. During pain testing, study subjects will sit in a comfortable chair in a low-ambient light room with their head positioned on a chinrest for continuous recording of pupil diameter using a near infrared recording system as described in preliminary data. Pupil diameter and probe temperature will be passed through an analog to digital converter and acquired at 60 Hz for subsequent analysis.

Five sequences of test stimuli will be presented, with a brief break in between each sequence (Figure 5A). The first sequence will consist of 7 stimuli, from 39° to 51° C in 2° C increments, in ascending order. Data from this training sequence will not be used for analysis. Sequences 2 and 3 will consist of 5, 5-sec stimuli, presented in random order, to generate moderate (50° C) and mild (47° C) pain (random condition). Sequences 4 and 5 will also consist of random presentation of 5 stimuli at these temperatures, but with different auditory tones 6 s prior to stimulus onset to correctly cue the stimulus temperature (cued condition).

Subjects will then be randomized to receive oral gabapentin, 900 mg, modafinil, 200 mg, or placebo, followed 2 hr later by pain testing with pupillometry, consisting of different sequences (Figure 5B). The random and cued paradigms will be presented twice each (only 1 representative shown in Figure 5B), followed by a sequence with one miscue in the positive expectation for pain direction (signal for 50° C but deliver 47° C) and one in the negative

Table 1. Questionnaires

Stanford Expectations of Therapy Scale
WOMAC- Osteoarthritis Index
Life Orientation Test-Revised (LOT-R)
PROMIS- Depression
PROMIS- Anxiety
Pain Medication Attitudes Questionnaire (PMAQ)
Pain Locus of Control Scale (PLOC)
Pain Self-Efficacy Scale (PSE)
Barratt Impulsivity Test
Fear of Pain Questionnaire
Pain Catastrophizing Scale (PCS)
Tampa Scale of Kinesiophobia (TSK)

[figure not shown]

Figure 4: The dimensional structure of the continuum of cognitive style to be used, including psychosocial constructs associated with each end.

expectation for pain direction (mistrust condition, yellow bars in Figure 5B). Subjects will provide verbal pain intensity scores after each stimulus.

The pre-drug and post-drug set of sequences will take approximately 30-40 min including breaks between sequences of stimuli. Following this subjects will be discharged from the clinical research unit accompanied by a responsible adult.

[figure not shown]

Figure 5: Heat stimuli give before (A) or after (B) study drug

Subject payment. Subjects will be paid \$250 for participation in the study.

Data analysis. Pupil diameter data will be conditioned to remove blink and saccade artifacts and smoothed using an autoregressive filter. The local resting diameter will be determined representing the average smoothed value for the 500 msec preceding the stimulus onset. The pupil response to each stimulus is calculated as the mean pupil diameter during the 5 sec stimulus after accounting for lag time from onset of stimulus to onset of pupil response and is expressed as a % change from the local resting diameter (see our preliminary data for examples). Multidimensional Scaling (MDS) will be used to create a single dimensional scale from the catastrophizing and optimism scores (i.e., responses from these two questionnaires will be weighted and scaled to create a single-dimensional construct)

To determine the interaction among the factors of interest, and to accommodate the many repeated measures within each participant, we will utilize Generalized Estimating Equations. In our experience, the pupil response to painful stimuli is well modeled by a normal distribution with an identity link and an AR1 repeated measures covariance structure. To examine our hypotheses, we will model percent pupil change (the DV) using fixed effects for stimulus temperature, catastrophizing-optimism score (i.e., cognitive-affective state), and pre-stimulus baseline pupil diameter (i.e., LC activity). The association between cognitive-affective state and pain reporting will first be examined, and in a later block the moderating effect of baseline pupil size will be entered.

The goal of this feasibility study is to estimate the effect size of drugs on pupil diameter and the strength of interaction between pupil diameter and the relationship between cognitive-affective state.

Expected results. We anticipate, based on preliminary data, that pain reporting will be weakly correlated with cognitive-affective state and that resting pupil diameter as a reporter of LC gain will interact with this correlation or tendency to apply cognitive style to pain reporting. We anticipate overall reduced pain reporting after placebo (placebo effect) and that the magnitude of this reduction and that of negative of pain will be inversely related to location on the optimism-catastrophizing continuum (i.e., greater placebo effect, greater effect of negative expectations of pain, and lesser effect of positive expectations of pain in strong optimists). After gabapentin or modafinil we anticipate that resting pupil diameter will be greater (i.e. greater tonic LC activity) than placebo. According to the gain concept, the effect of gabapentin on pain reporting across conditions should depend on cognitive-affective state, with overall reductions in pain reporting in strong optimists and amplification of pain in strong catastrophizers. The study is not powered to definitively show the effects of these drugs on either pupil diameter or its relationship to pain reporting as a function of optimism-catastrophizing. Rather, it is to provide feasibility, effect size, and variability data to support the choice of drug and power analysis for the eventual controlled study.

References

1. Alexander, JK, et al. Beta-adrenergic modulation of cognitive flexibility during stress. *J Cogn Neurosci* 2007;19:468-478.
2. Astafiev, SV, et al. Comment on "Modafinil shifts human locus coeruleus to low-tonic, high-phasic activity during functional MRI" and "Homeostatic sleep pressure and responses to sustained attention in the suprachiasmatic area". *Science* 2010;328:309-
3. Chapman, CR, et al. Phasic pupil dilation response to noxious stimulation in normal volunteers: relationship to brain evoked potentials and pain report. *Psychophysiology* 1999;36:44-52.
5. Geng, JJ, et al. A match made by modafinil: probability matching in choice decisions and spatial attention. *J Cogn Neurosci* 2013;25:657-669.
6. George, SA, et al. Altered locus coeruleus-norepinephrine function following single prolonged stress. *Eur J Neurosci* 2013;37:901-909.

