A Feasibility Study: Understanding and Altering Pain Expectations in Subjects With  
Osteoarthritis of the Knee or Hip  
Statistical Analyses Plan

NCT02155257

11/02/2018

To address the two primary hypotheses, linear mixed effects models will be employed. For each model, subject will be specified as a random effect to account for the repeated measures within individuals. To examine the impact of drug (i.e., placebo, gabapentin, modafanil) on tonic pupil diameter, pupil diameter will be regressed on fixed effects for drug, time (i.e., pre-drug vs post-drug), and a drug x time interaction. A group x time integration would be interpreted as evidence supporting the hypothesis that drug differentially impacted baseline pupil over time.

To examine the impact of tonic pupil diameter on the relationship between cognitive style (i.e., catastrophizing-optimism dimension) and pain reporting, VAS scores will be regressed on fixed effects for catastrophizing-optimism, tonic pupil diameter, and the interaction between catastrophizing-optimism x pupil diameter. A statistically significant interaction would be interpreted as evidence that tonic pupil diameter moderated the relationship between cognitive style and pain reporting. Where appropriate, all analyses are two-tailed with statistical significance interpreted at  $p < 0.05$ . The analyses will be conducted using R 3.4 and R Studio.

The sample size was based on estimating the feasibility of the protocol and on establishing effect size estimates. No formal statistical power calculations were conducted.

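### The style-dependent drug effect on pain that the protocol says it will examine is never estimated: no planned model contains both drug and pain

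*Protocol*

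**What the plan says.** In the protocol's Background, under the heading on gabapentin and modafinil, the study undertakes to examine modafinil's effect on pupil diameter and "its effect to alter pain reporting as a function of baseline state by increasing gain". Under Expected results, the gain concept is said to imply that "the effect of gabapentin on pain reporting across conditions should depend on cognitive-affective state", with less pain in strong optimists and more in strong catastrophizers.

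The data for this are collected. Questionnaires come before any experimental procedure. Pain is scored in the pre-drug sequences. "Subjects will then be randomized to receive oral gabapentin", modafinil or placebo, and testing is repeated 2 hr later. In the account of post-drug testing the protocol adds: "Subjects will provide verbal pain intensity scores after each stimulus".

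The planned analyses lie elsewhere. The protocol's Data analysis section says "we will model percent pupil change (the DV) using fixed effects for stimulus temperature, catastrophizing-optimism score" and pre-stimulus pupil diameter. It then relates style to pain reporting and adds that "in a later block the moderating effect of baseline pupil size will be entered". The SAP fits one model of pupil diameter on drug, time and their interaction. In a second, "VAS scores will be regressed on fixed effects for catastrophizing-optimism, tonic pupil diameter, and the interaction between catastrophizing-optimism x pupil diameter".

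**The concern.** The randomised factor and the pain outcome never meet in one model. Followed as written, the analysis would not produce an estimate of either drug's effect on pain, overall or by cognitive style, although the protocol says it will look at this and predicts its direction.

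The only planned test linking style to pain runs through pupil diameter, which is measured and not assigned. People with habitually larger pupils may report pain differently for reasons unrelated to the drugs. The SAP also does not say whether its pain model uses pre-drug, post-drug or pooled observations, and it has no time term, so drug-induced and between-person pupil differences are mixed. At stake is a secondary effect-size and variability estimate that the trial could supply at almost no cost.

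**Working it through.** **Inventory of planned models.**

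| Model | Outcome | Terms | Drug and pain together? |
|---|---|---|---|
| Protocol, Data analysis, GEE | percent pupil change | temperature, style, pre-stimulus pupil | no; has neither |
| Protocol, Data analysis, pain step | pain reporting | style, then pupil as moderator | no; drug not named |
| SAP, first model | tonic pupil diameter | drug, time, drug x time | no; no pain |
| SAP, second model | VAS pain | style, pupil, style x pupil | no; no drug, no time |

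Models with pain as outcome and drug as a term: 0 of 4.

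**The plan's own figure.** 3 arms x 10 = 30 agrees with the stated sample size. No power calculation is given, so there is nothing further to reproduce.

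**What the missing model could deliver.** Take one post-drug mean pain value per subject, adjusted for the pre-drug mean. The model has 7 coefficients: intercept, pre-drug pain, two drug contrasts, style and two drug x style terms. Residual df = 30 − 7 = 23, and t(0.975, 23) = 2.069. Let s be the residual SD and scale style to SD 1 (assumptions).

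- With the within-arm style SD exactly 1: SE of one arm's slope = s/√(10 − 1) = s/3. SE of the difference between two arms = s√2/3 = 0.471s. The half-width is 1.96 x 0.471s = 0.92s with the normal quantile, or 2.069 x 0.471s = 0.98s with t.
- With style sampled from a normal distribution: each arm's sum of squares is chi-square on 9 df, whose mean reciprocal is 1/(9 − 2) = 1/7. SE ≈ s√(2/7) = 0.535s. Half-width ≈ 2.069 x 0.535s = 1.11s.
- A simulation without the pre-drug covariate (24 df) gave a median half-width of 1.03s. With the covariate the mean is about 1.1s.

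If s is 1.0 to 1.5 points on the 0–10 scale (assumption), 1.11s is about ±1.1 to ±1.7 points per SD of style. Simulated power at two-sided 0.05, without the covariate, is about 17%, 48% and 78% for slope differences of 0.5, 1.0 and 1.5 residual SDs.

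**Can the style x pupil term stand in?** Simulate 30 subjects, 20 of them on active drug. Let a stable pupil trait moderate the style–pain slope (coefficient 0.5), and let the drug dilate the pupil by 0.5 SD without touching pain. Using subject means, style x pupil averaged 0.47 and the randomised style x drug term on pain change averaged 0.01. In a separate simulation with pre and post rows pooled and a random intercept, a drug effect on pain that truly depended on style gave style x pupil of 0.42. A clearly positive interaction therefore arises with or without any drug effect on pain, and the term alone cannot say which. The sizes depend on the assumed values; the ambiguity is the point.

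**The case against.** The strongest reply is that this was never a main question. Neither numbered hypothesis and neither primary outcome under Study Design concerns a drug effect on pain. The SAP confines itself to the primary hypotheses. The goal at the end of Data analysis names drug effects on pupil diameter and the pupil–style interaction only. The Background sentence names modafinil alone and leaves baseline state undefined; gabapentin rests on Expected results. All of this stands, and it sets the weight: an unanalysed secondary aim, not a missing primary analysis.

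A reader might infer more than the documents support in three ways.

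- That the gap compromises the choice of drug for the follow-on study. The explicit rule in the Background turns on whether gabapentin dilates the pupil, and the SAP's first model addresses that with the randomised contrast.
- That a drug which dilates the pupil and lowers pain equally in everyone would pass for one that raises gain. Under assumed SDs, uniform analgesia gave a pupil main effect of −0.58 and style x pupil of 0.00; a style-dependent effect gave 0.00 and 0.42. The SAP's second model does separate these two cases.
- That pupil variation is wholly unrelated to randomisation. If post-drug observations are included, part of it is caused by the assigned drug.

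Low power is also a fair remark. It does not answer the point, because Expected results disclaims definitive tests and asks for effect-size and variability data.

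**Conclusion.** The concern holds as a gap in a secondary aim. The protocol says it will examine a state-dependent effect of modafinil on pain and predicts one for gabapentin, the randomised pre/post pain data are collected, and 0 of 4 planned models would estimate it. The style x pupil model is no substitute, since it can be positive through stable between-person pupil differences alone. Reading baseline state as cognitive style is an interpretation, which Expected results supports.

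The size of what is forgone is modest: two drug x style estimates, each with a 95% interval of about ±1.1 residual SDs per SD of style. This assumes 10 analysable subjects per arm, normally distributed style scores and one summary pain value per subject per period. The primary hypotheses, the sample size and the drug-choice rule are untouched.

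**What to change.** Add one exploratory model to the SAP: post-drug mean pain per subject (random and cued sequences) on pre-drug mean pain from the same two conditions, drug (each active arm versus placebo), catastrophizing-optimism score, and drug x style. Centre the style score so that the drug effects are read at average style. Report the two drug and two drug x style estimates with 95% intervals, label them exploratory, and describe the style x pupil result as observational. If the investigators prefer not to do this, one sentence should say that the Background aim will not be analysed.

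Do not make a claim about the gain mechanism depend on the sign of the randomised slope alone. With no effect each drug would show the predicted sign half the time, and with a true slope difference of 0.5 residual SD it would miss it about 17% of the time (0.5/0.535 = 0.93 standard errors).

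The cost is SAP wording and one more analysis on data already collected. The downside is wide intervals, which should be presented as estimates and not as tests.

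### Neither the expectation effect (protocol hypothesis 2) nor the drug effect on response to noxious stimuli (part of primary outcome 1) has an analysis in the protocol or SAP

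*Protocol*

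**What the plan says.** The protocol's Study Design section gives two hypotheses. The first is that both drugs enlarge the resting pupil. The second is "Expectations will modify pain experience with a moderate effect size in these patients". The Background (Expectations alter pain experience) states the same aim for the clinical population: "to test whether we can manipulate expectations on pain in this population". Study procedures then sets out random, correctly cued and, after drug, miscued stimuli. Expected results predicts how positive and negative expectations will act along the optimism-catastrophizing scale.

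The two primary outcome measures are "Resting pupil diameter and response to noxious stimuli after study drug" and "Interaction between resting pupil diameter and correlation of cognitive-affective state to pain reporting".

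The SAP opens with "To address the two primary hypotheses, linear mixed effects models will be employed". Its first model is for tonic diameter: "pupil diameter will be regressed on fixed effects for drug, time", plus their interaction. Its second is for pain: "VAS scores will be regressed on fixed effects for catastrophizing-optimism, tonic pupil diameter", plus their interaction. The protocol's Data analysis section adds a GEE model of percent pupil change and a two-step analysis of pain reporting.

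**The concern.** The SAP's opening sentence invites the reader to pair its two models with the protocol's two hypotheses. The first pair fits. The second does not: a model of pain on cognitive style and pupil size cannot show whether cues changed pain, because it does not know which stimuli were cued.

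Primary outcome 1 has a similar gap. It has two components, resting diameter and response to noxious stimuli, and only the first is compared between drugs.

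The study exists to supply effect sizes and variability for a later trial. Without a stated estimator, the contrast, the trials used, the population and the variance structure for these two effects would all be chosen at analysis.

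**Working it through.** **Step 1. Terms in each specified analysis.** Four analyses are described.

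| Source | Outcome | Fixed effects listed | Cue or miscue term | Drug term |
|---|---|---|---|---|
| Protocol, Data analysis (GEE) | Percent pupil change | Temperature, catastrophizing-optimism score, pre-stimulus diameter | No | No |
| Protocol, Data analysis (pain) | Pain report | Cognitive-affective state; then moderation by baseline pupil | No | No |
| SAP, first model | Tonic pupil diameter | Drug, time, drug x time | No | Yes |
| SAP, second model | Pain (VAS) | Catastrophizing-optimism, tonic diameter, interaction | No | No |

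None of the four has a cue term. One has a drug term, with tonic diameter as outcome. One has pupil response as outcome, without drug or time. That gives no estimate for hypothesis 2 and none for the drug effect on pupil response.

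**Step 2. Data that the missing cue analysis would use** (Study procedures, reading 5 stimuli per sequence).
- Pre-drug: 2 x 5 random + 2 x 5 cued = 20 scores per subject; 20 x 30 = 600.
- Post-drug: both paradigms are again given twice, but the text does not give the number of stimuli per sequence, so they are not counted here.
- Miscues, post-drug only: one per direction, so 2 x 30 = 60 in all, 30 per direction.

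**Step 3. Precision to expect.** The plan states no effect size or SD, so there is no figure to reproduce. Assume d = 0.5 as one reading of a moderate effect. For the cue effect, d is the mean within-subject difference divided by the SD of subjects' differences.

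Within-subject: SE = sqrt(1/n + d²/(2n)); CI = d ± t × SE on n - 1 df.
- n = 30: SE = sqrt(0.0333 + 0.0042) = 0.194; t = 2.045; CI 0.10 to 0.90.
- n = 20: SE = sqrt(0.0500 + 0.0063) = 0.237; t = 2.093; CI 0.00 to 1.00.
- n = 10: SE = sqrt(0.1000 + 0.0125) = 0.335; t = 2.262; CI -0.26 to 1.26.

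Three values of n are shown because hypothesis 2 concerns patients, while the study also enrols healthy people without pain and does not give the split.

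One drug against placebo, 10 v 10: SE = sqrt(2/10 + d²/40) = sqrt(0.2000 + 0.0063) = 0.454; t = 2.101 on 18 df; CI -0.45 to 1.45.

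**The case against.** The best defence is that the plan does what its stated goal requires. Data analysis limits the goal to the drug effect on pupil diameter and the interaction of pupil diameter with cognitive-affective state, and the SAP's two models are exactly those. The rule for choosing the later trial's drug rests on pupil dilation. The sentence on effect size and variability in Expected results follows one about the drug effects, so it does not plainly promise an estimate for every hypothesis. The study is openly unpowered. All of this stands, and it makes the fault one of alignment: hypotheses, outcomes, goal and SAP do not match. Lack of power explains wide intervals, not the absence of an estimator for a stated hypothesis and for part of a primary outcome.

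The protocol also introduces its GEE as the way to examine its hypotheses. The effects it then lists include neither cue condition nor drug.

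It may be said that response to noxious stimuli means pain rather than pupil response. The wording allows that, but no pain model has a drug term either, so the gap remains on both readings.

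A reader might infer that a primary hypothesis was dropped, perhaps once results were known. The documents do not support this. The protocol does not label hypothesis 2 as primary, the protocol's own analysis section already lacked a cue term, and the SAP (dated 11/02/2018) does not say whether data had been seen.

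**Conclusion.** The point holds in this form. Followed as written, the plan yields no estimate of the expectation effect and none of the drug effect on pupil response. This follows from the listed model terms and needs no assumption. The sizes in Step 3 rest on the assumed d of 0.5 and, for the cue effect, on how many subjects are patients. They show how imprecise the added estimates would be; they do not establish the gap.

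A reader might also infer that the drug comparison as a whole lacks an analysis. It does not: the missing terms leave the SAP's drug-by-time model of resting diameter untouched. The matter should be fixed, but it does not undermine the study's narrower stated goal.

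**What to change.** All changes are to SAP wording.

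(a) **Expectation effect.** Model pain score on cue condition (random, correctly cued, miscued up, miscued down) and delivered temperature, adding drug and time when post-drug data are used. Include a subject random intercept and a by-subject cue slope, or analyse per-subject paired differences. Estimate the effect in the osteoarthritis patients, or with a patient/healthy-by-cue term, and show the pooled estimate separately. Report the effect size, 95% CI and between-subject variance. Label pre-drug random versus cued as cue plus order, because the random sequences always come first. Label the miscue contrast as post-drug, with one miscue per direction per subject.

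(b) **Drug effect on response.** Add a drug-by-time model of pupil response with delivered temperature, through per-subject pre-post change or a by-subject time slope, using the random and cued sequences given at both times. Report absolute change in mm beside the protocol's percent change, because the drugs are expected to alter the resting diameter that forms the denominator. With assumed values, the same 0.5 mm dilation is 10.0% of a 5.0 mm pupil but 9.1% of a 5.5 mm pupil. Do not adjust the main estimate for post-drug resting diameter. State whether the outcome means pupil response, pain response or both; if pain is included, report its drug-by-time estimate too.

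(c) **Alignment.** Tie the SAP's second model to primary outcome 2, list hypothesis 2 separately, and mark (a) and (b) as estimation. Call them pre-specified only if added before the data are examined; otherwise label them as added later.

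The cost is two or three more imprecise estimates in an unpowered study. A random-slope model may fail to converge; per-subject differences avoid that. Procedures and sample size do not change.
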